4. STUDY DESIGN

4.1. Overall design

See Section 1.2 for the study schematic diagram.

This study will be a combination of retrospective and prospective cohort design with two groups. RSVPreF3 vaccine group will include participants who received RSVPreF3 vaccine in RSV MAT studies and control group will include participants who received any control (placebo, Tdap or influenza vaccine) during *prior* RSV MAT studies.

- **Retrospective cohort**

- Current study participants who are more than 2 years after vaccination/control and are not currently pregnant at the time of study enrollment will be included in this study cohort.
 - Participants previously enrolled in *prior* RSV MAT studies will be included in this cohort.
 - For participants enrolled in prior studies of pregnant women (i.e., MAT-004, MAT-009, MAT-012), data collection for this cohort will not include the prior study pregnancy.
- Medical data related to any pregnancy conceived post RSVPreF3 vaccine or any control (placebo, Tdap or influenza vaccine) through study enrollment (even if the pregnancy was conceived after 2 years post-vaccine/control) will be collected retrospectively from the date of start of current study pregnancy up to Day 42 (approximately 6 weeks) post-delivery.
- Infants will be enrolled with the maternal participants at Visit 1 and all relevant medical data until Day 42 post-delivery will be retrieved.

- **Prospective cohort:**

- Current study participants who are within 2 years+2 months after vaccination/control or with ongoing pregnancies (pregnancies prior to Day 42 post-delivery) at the time of study enrollment will be included in this study cohort.
- Study participants enrolled in *prior* RSV MAT studies will be included in this study cohort.
 - For participants enrolled in prior studies of pregnant women (i.e., MAT-004, MAT-009, MAT-012), data collection for this cohort will not include the prior study pregnancy.
- All participants will be followed up for 2 years+2 months post RSVPreF3 or control vaccination to record any pregnancy conceived within 2 years post vaccine/control. If the participant is pregnant at 2 years post-vaccine/control, study follow-up will continue until day 42 post-delivery.

Note: Pregnancies reported during prospective follow-up at approximately 2 years+2 months that were conceived after 2 years post-vaccine/control will not be included in the study.

- Medical data related to any pregnancy conceived post RSV MAT (RSVPreF3) vaccine and any control (placebo, Tdap or influenza vaccine) will be collected from the date of start of current study pregnancy up to day 42 (approximately 6 weeks) post-delivery.
- Infants will be enrolled at Delivery and all relevant medical data until Day 42 post-delivery will be collected.
- **Type of study and design:** A safety follow-up cohort study.
- **Study period:** *The* study period starts from the date of start of any pregnancy conceived after RSV MAT vaccination (RSVPreF3) or control vaccination in RSV MAT studies or from the date of current study enrollment, whichever date is earlier. The study period ends at current study enrollment for retrospective cohort participants. The study period ends at 2 years+2 months post vaccine/control for prospective cohort participants who are not pregnant at 2 years post vaccine/control. The study period ends at Day 42 post-delivery for prospective cohort participants who are pregnant at 2 years post vaccine/control **or at study enrollment.**
- **Number of participants:** All adolescent or adult study participants (approximately 8240) from the above-mentioned RSV MAT studies will be considered for enrollment based on the eligibility criteria. Approximately 650 enrolled study participants are estimated to have at least one pregnancy of interest for this study (see Section 9.5 for detailed calculations). Even approximately 300 participants with pregnancy information included in the study would still provide reasonable precision to detect and estimate most of the events of interest in the study.

4.2. Scientific rationale for study design

See Section 2.1 and Section 2.2.

4.2.1. Participant input into design

Not applicable

4.3. Justification for dose

Not applicable

4.4. End-of-study definition

A participant is considered to have completed the study if the participant has completed all periods of the study including the last contact (study conclusion). This last contact can be either 1) at current study enrollment for retrospective cohort participants, 2) at 2 years+2 months post vaccine/control for prospective cohort participants who are not pregnant at 2 years post vaccine/control, or 3) at Day 42 post-delivery for prospective

cohort participants who are pregnant at 2 years post vaccine/control ***or who are pregnant at enrollment***. The study may be terminated earlier if other research demonstrates no impact of vaccination on pregnancies conceived post-vaccination.

4.5. Study limitations

- The study participants who decide to enroll in this study are already aware whether they received RSVPreF3 or control. Study participants from prior RSV MAT pregnancy studies who experienced an adverse pregnancy outcome or a pregnancy/infant event from a prior pregnancy, may choose to participate in the current study at different rates than those who did not. This may lead to selection bias. As we have information on prior vaccination/control and prior adverse events/outcomes, we can evaluate whether this occurs and consider statistical analysis approaches to adjust for this.
- Comparison between incidence of events or outcomes in this study and events or outcomes in previous RSV MAT studies likely cannot be made directly because of the following possible limitations: 1) the expected sample size for this study is too small for the study to be adequately powered for comparisons, 2) this study has different inclusion and exclusion criteria, 3) this study has different timepoint of pregnancy at enrollment (as early as possible), and 4) different risk factors for participants in this study, such as a relatively short inter-pregnancy interval for pregnancies included in this study.
- This study includes two cohorts, one for which ***all*** data will be collected retrospectively and the other cohort for which data will be collected prospectively (***with some retrospective data collection***). This approach was taken so that the number of enrolled participants can be maximized. However, this may result in underestimation of the true incidence of AESIs in a pooled cohort (retrospective and prospective), as the retrospective cohort is more subject to recall bias.
- This study is conducted with a proportion of the same participants enrolled in previous RSV MAT studies which uncovered a safety signal, as described in Section 2.2. As there is still no plausible mode of action or known imbalance in risk factors across RSVPreF3 vs. control groups identified that explains the safety signal, the possibility remains there is unknown confounding (an unmeasured risk factor or exposure) leading to the safety signal. If there is unknown confounding, that may lead to a similar safety finding in this study.

5. STUDY POPULATION

Prospective approval of protocol deviations to recruitment and enrollment criteria, also known as protocol waivers or exemptions, is not permitted.

The study population will include up to 8240 participants (***those who had conceived before study enrollment, those with ongoing pregnancy or who at enrollment may not have conceived but are followed for conception within 2 years post vaccine/control***) from RSV MAT studies to collect pregnancy outcome, pregnancy related AESIs and infant AESIs for any pregnancy conceived post-vaccination (***refer Section 9.5***).

All study participants who have received either RSVPreF3 vaccine or control (placebo, Tdap only, influenza vaccine only) will be included in this study.

Study participants with any pregnancy conceived after vaccination with Day 42 post-delivery at or before study start (i.e., any pregnancy conceived after vaccination is a past pregnancy) will be included in the retrospective cohort and retrospective data will be collected from medical records.

Study participants with any pregnancy conceived after vaccination ongoing at study start (pregnancy prior to Day 42 post-delivery) or newly reported during current study follow-up will be included in the prospective cohort and relevant data will be collected from medical records, as identified through structured follow-up contacts.

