5.1. Inclusion criteria

5.1.1. Retrospective cohort

Adult/Adolescent Participant:

- Adult/Adolescent study participant, from *any of the prior RSV MAT* studies who have either received RSV MAT vaccine or control (placebo, Tdap or influenza vaccine).
- Study participant:
 - Who has reached 2 years+2 months post vaccine/control prior to/at enrollment or
 - who has not reached 2 years+2 months post vaccine/control prior to/at enrollment but is a Woman of Nonchildbearing Potential (WONCBP) as defined in Section 10.3.1.2 at study enrollment, or recipient of bilateral tubal ligation prior to study enrollment.
- Study participant with any pregnancy conceived post-vaccination/control, that has reached Day 42 post-delivery prior to/at enrollment.
- Provide signed and dated informed consent form.
- Be willing to comply with all study requirements and be available for the duration of the study.

Infant Participant:

- Participant live born as the result of a pregnancy followed in an adult/adolescent participant in this study.
- Signed and dated informed consent form obtained from the participant's parent(s)/LAR(s) prior to performance of any study-specific procedure.

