5.1.2. Prospective cohort

Adult/Adolescent Participant:

- Adult/adolescent study participant from ***any of the prior RSV MAT*** studies who have either received RSV MAT vaccine or control (placebo, Tdap or influenza vaccine).
- Study participant:
 - Who has not reached 2 years+2 months post vaccine/control prior to/at enrollment or
 - Who has reached at least 2 years+2 months post vaccine/control but has an ongoing pregnancy (prior to Day 42 post-delivery) at enrollment. Participants who have reached 2 years post-vaccine/control before enrollment but are pregnant at enrollment will be enrolled and followed until Day 42 post-delivery for the pregnancy ongoing at enrollment.
- Female participants of childbearing potential.
- Provide signed and dated informed consent form.
- Be willing to comply with all study procedures and be available for the duration of the study.

Infant Participant:

- Participant live born as the result of a pregnancy followed in an adolescent/adult participant in this study.
- Participant's parent(s)/LAR(s), in the opinion of the investigator, can and will comply with the requirements of the protocol.
- Signed and dated informed consent form obtained from the participant's parent(s)/LAR(s) prior to performance of any study-specific procedure.

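### Protocol Sections 4.1, 5 and 5.1 assign cohorts by non-equivalent rules; a site following Section 5 would stop following some women before their 2-year conception window closes

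*Protocol*

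**What the plan says.** Three places in the protocol state who belongs to which cohort.

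- **Section 4.1.** Retrospective: "Current study participants who are more than 2 years after vaccination/control and are not currently pregnant at the time of study enrollment". Prospective: those "who are within 2 years+2 months after vaccination/control or with ongoing pregnancies (pregnancies prior to Day 42 post-delivery) at the time of study enrollment".
- **Section 5.** The retrospective cohort takes women with "any pregnancy conceived after vaccination with Day 42 post-delivery at or before study start", with no condition on time since vaccination. The same sentence continues: "any pregnancy conceived after vaccination is a past pregnancy) will be included in the retrospective cohort". The next paragraph sends pregnancies that are ongoing at study start, or newly reported in follow-up, to the prospective cohort.
- **Section 5.1.** Retrospective (5.1.1): a woman "Who has reached 2 years+2 months post vaccine/control prior to/at enrollment", or one inside that limit who is of nonchildbearing potential (WONCBP) or has had a bilateral tubal ligation. In either case she must also have a pregnancy that has passed Day 42. Prospective (5.1.2): a woman of childbearing potential "Who has not reached 2 years+2 months post vaccine/control prior to/at enrollment", or one past that limit with a pregnancy still before Day 42.

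The label decides follow-up. Section 4.1 states: "The study period ends at current study enrollment for retrospective cohort participants", and Section 4.4 agrees. A prospective participant who passes Day 42 before 2 years+2 months goes back to six-monthly contacts until then (Figure 2 footnote). Table 2 footnote b allows a past pregnancy to be recorded at her first visit.

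**The concern.** A woman of childbearing potential who enrolls inside 2 years with one completed post-vaccination pregnancy is retrospective under Section 5 and prospective under Section 5.1. If the site uses Section 5, she is closed on the day she enrolls, and a second pregnancy conceived before 2 years is never recorded.

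The first secondary endpoint counts any pregnancy conceived within 2 years, so that pregnancy should be in it. What goes missing is a repeat pregnancy, with both conceptions inside the same 2 years. It can therefore easily fall under the 18-month inter-pregnancy interval that the plan names as a risk factor (Protocol 9.3.3.2, SAP 4.3.2.2). Cohort is also a planned stratifier of the primary and secondary endpoints (SAP 4.6.2.3), so unclear assignment also blurs that comparison.

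**Working it through.** **The plan's own figure.** Table 4 sets 2 years+2 months at 790 days: 2 × 365 + 60 = 790. The 2-year conception window is 730 days, leaving a recognition buffer of 790 − 730 = 60 days.

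**Rules side by side.** I applied each section literally to 12 profiles of women of childbearing potential: day 400, 760 or 900 since vaccine/control, crossed with never pregnant, past Day 42, delivered but before Day 42, and pregnant. Five profiles get the same cohort from all three sections. The other seven are below (R = retrospective, P = prospective).

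| Day | Status at enrollment | Section 4.1 | Section 5 | Section 5.1 |
|---|---|---|---|---|
| 400 | never pregnant | P | not placed | P |
| 400 | past Day 42 | P | R | P |
| 760 | never pregnant | R and P | not placed | P |
| 760 | past Day 42 | R and P | R | P |
| 760 | delivered, before Day 42 | R and P | P | P |
| 900 | never pregnant | R | not placed | neither |
| 900 | delivered, before Day 42 | R and P | P | P |

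The day-400 never-pregnant row is only silence in Section 5. The day-400 past-Day-42 row is the contradiction that cuts off a large part of the window. The rows showing both cohorts come from Section 4.1 alone.

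**Size of the unfollowed window under Section 5.** Window lost = 730 − enrollment day.

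- Day 400: 730 − 400 = 330 days.
- Day 600: 730 − 600 = 130 days.
- Ceiling: vaccination stopped on 28 February 2022 (Section 2.2) and the assumed study start is 7 December 2022 (Section 9.5), 282 days later. 730 − 282 = 448 days. This needs a pregnancy that ended by day 282 − 42 = 240, so it is an extreme.

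At the assumed start, anyone vaccinated after about 7 December 2020 was still inside 2 years, so the situation is reachable. The documents do not give the distribution of vaccination or enrollment dates, so the number of women cannot be computed.

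**Section 5.1 on its own.** Each of the 12 profiles falls in at most one cohort, and none inside 790 days is retrospective. Two gaps remain:

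- A woman past 790 days with one completed and one ongoing pregnancy meets both 5.1.1 and 5.1.2.
- A WONCBP woman inside the window with a completed pregnancy is retrospective under 5.1.1 even if she plans IVF, although 5.2 would not exclude her from the prospective cohort. If her pregnancy has not reached Day 42, she meets neither 5.1.1 nor 5.1.2.

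**Timing word.** Section 5 tests status at study start, which Section 10.1.9 defines at country level. Section 5.1 tests it at the woman's enrollment.

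**The case against.** The strongest reply is that Section 5.1 is the formal rule and Section 5 is introductory. The glossary ties eligibility to strict adherence to the inclusion and exclusion criteria. The Figure 1 and 2 footnotes and Table 2 footnote b follow 5.1, Table 3 provides for consent of an infant from a past pregnancy, and Section 4.5 says the prospective cohort includes some retrospective data. Sample size cites 5.1.1 and 5.1.2, and the Full Analysis Set cites 5.1. On that view, closing a fertile woman at day 400 would be a protocol deviation.

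Most of this stands, and it narrows the point to wording. It does not remove it. Section 5 says such women will be included in the retrospective cohort, and nothing states that 5.1 prevails over it. Its paragraph on newly reported pregnancies does not rescue the case, because a woman closed at enrollment has no follow-up in which to report one.

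Three stronger readings are tempting but not supported:

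- *Postpartum data are lost inside the 2-year window.* Section 5 requires Day 42 to have passed, and 4.1 makes women under 2 years prospective. The Day 42 ambiguity concerns women beyond 2 years who have delivered recently. They are not currently pregnant under 4.1's first bullet, yet its second bullet counts them as ongoing.
- *The primary endpoint is compromised.* In the Section 5 case the first pregnancy is already complete and is collected.
- *Women with an early completed pregnancy are the most likely to conceive again, or sites have already diverged.* The documents give no evidence for either.

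**Conclusion.** The contradiction is real and should be corrected, as a wording inconsistency with a specific consequence. The consequence inside the 2-year window comes from Section 5 alone: it would end follow-up of a woman of childbearing potential with up to 730 minus her enrollment day of eligible conception time left. The endpoint exposed is the secondary any-pregnancy one, plus the cohort stratification.

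The overlap in Section 4.1 between days 730 and 790 is a smaller matter. If such a woman is taken as retrospective, only a conception shortly before 2 years and not yet recognized can be missed, which is what the 60-day buffer was added to prevent.

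The conclusion assumes that at least some sites read Section 5 as an assignment rule. The documents do not show whether any did, how many women that would involve, or whether it would differ by study arm.

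**What to change.** 1. State in Section 5.1 that it is the only cohort rule and is applied at enrollment.
2. Replace the assignment wording in Section 4.1, and the two paragraphs of Section 5 that assign by past versus ongoing pregnancy, with a cross-reference to 5.1. A cross-reference keeps 5.1.1's completed-pregnancy condition; rewriting 4.1 without it would leave a never-pregnant woman at day 900 retrospective there and in neither cohort under 5.1.
3. Use enrollment, not study start, wherever cohort is decided.
4. Add to 5.1.1 that no post-vaccination pregnancy is ongoing (before Day 42 post-delivery) at enrollment, so that a woman past 2 years+2 months with one completed and one ongoing pregnancy is prospective only.
5. State that a woman under 2 years+2 months with only past pregnancies is prospective and followed to 2 years+2 months, unless she enters through the WONCBP/tubal ligation branch of 5.1.1.
6. Reconcile that branch with 5.1.2 and 5.2 for women who plan further conception, and for those whose pregnancy has not reached Day 42.

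The cost is a few lines of protocol text and a site memo. The women concerned would have continued six-monthly contacts instead of being closed at enrollment.

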5.1. Inclusion criteria

5.1.1. Retrospective cohort

Adult/Adolescent Participant:

- Adult/Adolescent study participant, from *any of the prior RSV MAT* studies who have either received RSV MAT vaccine or control (placebo, Tdap or influenza vaccine).
- Study participant:
 - Who has reached 2 years+2 months post vaccine/control prior to/at enrollment or
 - who has not reached 2 years+2 months post vaccine/control prior to/at enrollment but is a Woman of Nonchildbearing Potential (WONCBP) as defined in Section 10.3.1.2 at study enrollment, or recipient of bilateral tubal ligation prior to study enrollment.
- Study participant with any pregnancy conceived post-vaccination/control, that has reached Day 42 post-delivery prior to/at enrollment.
- Provide signed and dated informed consent form.
- Be willing to comply with all study requirements and be available for the duration of the study.

Infant Participant:

- Participant live born as the result of a pregnancy followed in an adult/adolescent participant in this study.
- Signed and dated informed consent form obtained from the participant's parent(s)/LAR(s) prior to performance of any study-specific procedure.

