Child in care	A child who has been placed under the control or protection of an agency, organization, institution or entity by the courts, the government or a government body, acting in accordance with powers conferred on them by law or regulation. The definition of a child in care can include a child cared for by foster parents or living in a care home or institution, provided that the arrangement falls within the definition above. The definition of a child in care does not include a child who is adopted or has an appointed legal guardian.
Eligible	Qualified for enrollment into the study based upon strict adherence to inclusion/exclusion criteria.
Essential documents	Documents which individually and collectively permit evaluation of the conduct of a study and the quality of the data produced.
GAIA	Global Alignment of Immunization Safety Assessment in pregnancy. A project that aims to improve the quality of outcome data from clinical vaccine trials in pregnant women with a specific focus on the needs and requirements for safety monitoring in low to middle income countries.
Investigator	
A person responsible for the conduct of the clinical study at a study site. If a study is conducted by a team of individuals at a study site, the investigator is the responsible leader of the team and may be called the principal investigator.
 
The investigator can delegate study-related duties and functions conducted at the study site to qualified individual or party to perform those study-related duties and functions.

Legally acceptable representative	
An individual, judicial or other body authorized under applicable law to consent on behalf of a prospective participant to the participant's participation in the clinical study.
 
The terms legal representative or legally authorized representative are used in some settings.

Term	Definition
Participant	
Term used throughout the protocol to denote an individual who has been contacted to participate or who participates in the clinical study as a recipient of the study intervention (vaccine(s)/product(s)/control).
 
Synonym: subject

Participant number	A unique identification number assigned to each participant who consents to participate in the study.

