9.3. Statistical analyses

9.3.1. General considerations

All statistical analyses are descriptive. Besides the primary analyses, sub-group analyses may be conducted.

All primary and secondary analyses will be performed on the ***Full Analysis Set***.

9.3.2. **Primary endpoints analysis**

	Primary Endpoints	Statistical Analysis Methods
Maternal participants	Number and percentage of maternal participants reporting pregnancy outcomes and pregnancy related AESIs within the first pregnancy conceived within 2 years post-vaccination in participants enrolled in prior RSV MAT studies up to Day 42 post-delivery.	The number and percentage of maternal participants reporting pregnancy outcomes and pregnancy related AESIs within the first pregnancy conceived within 2 years post-vaccine/control will be tabulated with its exact 95% CI by study arms. By participant listings of pregnancy related outcomes and AESIs will be prepared
Infant participants	Number and percentage of infant participant reporting infant AESIs from the first pregnancy conceived within 2 years post-vaccination in participants enrolled in prior RSV MAT studies up to Day 42 post-delivery.	The Number and percentage of infant participant reporting infant AESIs from the first study pregnancy conceived within 2 years post-vaccine/control will be tabulated with its exact 95% CI by study arms. By participant listings of infant AESIs will be prepared.

Pregnancy outcomes include (not limited to) spontaneous abortion, stillbirth, and preterm birth. The pregnancy related adverse events of special interest (AESIs) and infant AESIs are listed in Section 8.4.5.1.

9.3.3. **Secondary endpoints analyses**9.3.3.1. **Pregnancy outcomes and AESIs from any study pregnancy**

	Secondary Endpoints	Statistical Analysis Methods
Maternal participants	Number and percentage of maternal participants reporting pregnancy outcomes and pregnancy related AESIs during any study pregnancy conceived within 2 years post-vaccination in participants enrolled in prior RSV MAT studies up to Day 42 post-delivery.	The number and percentage of maternal participants reporting pregnancy outcomes and pregnancy related AESIs during any pregnancy conceived within 2 years post-vaccination in participants enrolled in prior RSV MAT studies up to Day 42 post-delivery , will be tabulated with its exact 95% CI by study arms on subject level. By participant listings of pregnancy related outcomes and AESIs will be prepared.

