9.5. Sample size determination

All analyses will be descriptive and thus no hypothesis driven sample size calculation was conducted.

As noted in Section 4.1, all study participants (approximately 8240) from prior RSV MAT studies will be considered for enrollment in this study based on the eligibility criteria. Assuming the study will start on December 7th, 2022, the study potential subjects include: (1) those who had deliveries defined in Section 5.1.1 (to be enrolled to Retrospective cohort); (2) those with ongoing pregnancy, or who at enrollment have not conceived but subsequently conceive within two years since the vaccination/control in previous RSV MAT studies as defined in in Section 5.1.2 (to be enrolled to Prospective cohort). The actual sample size will mainly depend on: (1) the enrollment rate of those subjects who participated in the previous RSV MAT studies; (2) the incidence rate of pregnancy conceived post RSVPreF3 (or control) vaccination during study period.

To estimate the incidence rate of first pregnancy conceived post RSVPreF3 (or control) vaccination, we considered the likelihood of pregnancy among participants in prior studies of non-pregnant women and pregnant women separately (approximately 8240 total). Among non-pregnant women (approximately 2540), we estimate approximately 10% will have a pregnancy during the time period of this study [Curtin, 2013]. Assuming 60% enroll in this study, we estimate approximately 150 non-pregnant women in prior studies who enroll in this study will have a pregnancy. Among pregnant women (approximately 5700), we estimated approximately 50% would have another pregnancy. From data on inter-pregnancy intervals in US women, we estimated approximately 30% of those subsequent pregnancies will occur during the time period of this study [Thoma, 2016]. Assuming 60% enroll in this study, we estimate approximately 500 non-pregnant women in prior studies who enroll in this study will have a pregnancy. In total, we estimate approximately 650 enrolled study participants will have at least one pregnancy of interest for this study and contribute to the total number of pregnancies from which incidence rates for events will be calculated.

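### Read literally, Protocol 5.1.1 leaves some women whose post-vaccination pregnancies all ended in miscarriage or termination with no route into the study, although these are primary outcomes; Sections 4.1 and 5 point the other way

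*Protocol*

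**What the plan says.** Protocol 5.1.1 sets as a separate inclusion criterion for the retrospective cohort: "Study participant with any pregnancy conceived post-vaccination/control, that has reached Day 42 post-delivery prior to/at enrollment". The woman must also be past 2 years+2 months or, if earlier, be of nonchildbearing potential or have had a tubal ligation. Section 9.5 describes the cohort as "those who had deliveries defined in Section 5.1.1 (to be enrolled to Retrospective cohort", and SAP section 5 repeats this. Section 8.4.5.2 likewise treats a pregnancy as completed once it is through Day 42 after delivery.

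The prospective cohort (5.1.2) has two timing routes. One takes a woman "Who has not reached 2 years+2 months post vaccine/control prior to/at enrollment or", the other a woman "Who has reached at least 2 years+2 months post vaccine/control but has an ongoing pregnancy (prior to Day 42 post-delivery) at enrollment". Both also require childbearing potential.

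The list of terms defines eligible as "Qualified for enrollment into the study based upon strict adherence to inclusion/exclusion criteria", and Section 5 states: "Prospective approval of protocol deviations to recruitment and enrollment criteria, also known as protocol waivers or exemptions, is not permitted".

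On outcomes, Protocol 9.3.2 says: "Pregnancy outcomes include (not limited to) spontaneous abortion, stillbirth, and preterm birth". SAP 4.2.1 also lists elective or therapeutic termination. Both documents define the maternal Full Analysis Set through Protocol 5.1, and SAP 4.2.2 calculates the primary outcome percentages on that set.

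Other text is broader. Section 4.1 describes retrospective participants as more than 2 years after vaccination and not pregnant, with no delivery condition, and collects data on any pregnancy. The Section 5 sentence on this cohort keeps the delivery anchor but explains it as meaning that the pregnancy lies in the past.

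**The concern.** A miscarriage or termination has no delivery in ordinary usage. Neither document extends the word to cover them or gives a Day 42 rule for a pregnancy that ends without a delivery. Under the literal criterion, entry to the retrospective cohort therefore depends on the outcome being measured.

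The stake is a primary safety result. Loss and termination percentages would be too low in the retrospective cohort and in the pooled figure, and absolute differences between arms would shrink. If some sites follow 5.1.1 and others 4.1, ascertainment of losses would also vary by site. The limitations in Section 4.5 cover volunteer selection and recall bias but not this selection.

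**Working it through.** **1. Which women have a route?** Take women whose post-vaccination pregnancies have all ended in miscarriage or termination, except in the last row.

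| Situation at enrollment | 5.1.1 as written | 5.1.2 | Result |
|---|---|---|---|
| Past 2 years+2 months, not pregnant | fails: no delivery | fails both timing routes | no route |
| Within the window, nonchildbearing potential | fails: no delivery | fails childbearing-potential criterion | no route |
| Within the window, childbearing potential | not applicable | first route | prospective |
| Past the window, pregnant again | not applicable | second route | prospective |
| Past the window, not pregnant, also had a qualifying delivery | met | not needed | retrospective |

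In the last row the delivery may come before or after the loss. If after, the loss is her first pregnancy and counts in the primary endpoint. If before, it counts only in the any-pregnancy secondary endpoint.

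**2. The plan's expected denominator (Protocol 9.5).** 2540 × 0.10 × 0.60 = 152.4, and 5700 × 0.50 × 0.30 × 0.60 = 513.0. The total is 665.4, against a stated figure of about 650. It reproduces to within 3%. The projection makes no deduction for excluded losses.

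**3. Model.** Three inputs are needed, and the documents give none of them, so all are assumptions:
- L: true share of first pregnancies ending in miscarriage or termination
- r: share of women with a study pregnancy who fall under the retrospective rules
- q: share of those losses in women with no other qualifying delivery

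The excluded fraction is r × L × q. The observed pooled rate is (L − rLq) / (1 − rLq).

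**4. Results for L = 15%**

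| r | q | rLq | Observed pooled rate | Women excluded of 650 |
|---|---|---|---|---|
| 0.25 | 0.50 | 0.01875 | 0.13125 / 0.98125 = 13.4% | 12 |
| 0.50 | 0.75 | 0.05625 | 0.09375 / 0.94375 = 9.9% | 37 |
| 0.75 | 1.00 | 0.11250 | 0.03750 / 0.88750 = 4.2% | 73 |

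In the same three scenarios, L = 10% gives 8.9%, 6.5% and 2.7%, and L = 20% gives 17.9%, 13.5% and 5.9%.

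In the retrospective cohort alone (r = 1) with L = 15%, the rate is 8.1% at q = 0.5, 4.2% at q = 0.75 and 0% at q = 1.

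The smaller denominator slightly raises other per-pregnancy rates. In the middle scenario a 5% rate becomes 5 / 0.94375 = 5.3%.

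**5. Between arms**
- *Equal r and q, no true effect:* both arms fall equally.
- *Equal r = 0.5 and q = 0.75, true rates 22.5% and 15.0%:* observed 15.4% and 9.9%. The difference falls from 7.5 to 5.4 points, while the ratio moves only from 1.50 to 1.55.
- *Unequal share (r = 0.3 against 0.6), q = 0.75, L = 15%, no true effect:* observed 12.0% against 8.8%, a spurious ratio of 1.36.

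**6. What drives r.** Protocol Table 4 sets 2 years+2 months at 790 days. From the assumed start on 7 December 2022, 790 days back is 8 October 2020. Vaccination stopped on 28 February 2022 (Section 2.2), so by 28 April 2024 every woman would be past the window. The retrospective share therefore grows the later women are enrolled.

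**The case against.** The strongest reply is that the documents use Day 42 after delivery as a general end marker for every pregnancy. The primary endpoint runs to that day for all outcomes, miscarriage included, so a strict reading would leave the window undefined for losses in both cohorts. Section 4.1 has no delivery condition, and Section 5 explains the phrase as a past pregnancy. Table 1 records pregnancy outcomes for the retrospective cohort. Sections 8.4.8.2 and 10.2.2 give reporting rules for terminations, spontaneous abortion and ectopic pregnancy. SAP 4.6.2.3 examines the primary endpoints by arm and cohort, so a shortfall of losses would show.

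Much of this stands: the broader intent is the more likely one, and the problem is an inconsistency in the text rather than a deliberate exclusion. But 5.1.1 is the operative criterion, strict adherence is required, and Sections 8.4.5.2 and 9.5 and SAP section 5 repeat the delivery anchor. The cohort analysis would expose a deficit but not correct it. Different wording was available: Protocol Table 15 times maternal death from the end of the pregnancy.

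A reader might infer that no loss can appear in the retrospective cohort, or that the study cannot observe losses. The documents support neither, because any other qualifying delivery opens the retrospective route and two groups of women can enter prospectively. Stillbirth involves a delivery and is not affected. Nor do the documents show that women were in fact turned away.

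**Conclusion.** The point holds conditionally. The passages conflict, and under the literal reading a defined group of women has no route into the study. If sites apply 5.1.1 as written, the pooled loss and termination rate is too low whenever the retrospective share is above zero and some of those losses have no other qualifying delivery to bring the woman in. For an assumed true 15%, the three scenarios give 13.4%, 9.9% and 4.2%. The last is the extreme for its share, since it assumes that no woman with a loss qualifies through another delivery.

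Absolute between-arm differences shrink. A spurious contrast needs a further condition, such as a retrospective share that differs by arm. If sites apply the broader wording of 4.1, this bias does not arise, but the text still does not tell them to.

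**What to change.** In Protocol 5.1.1, count Day 42 from the end of the pregnancy, whatever its outcome, instead of from delivery. Align Protocol 4.1, 5, 8.4.5.2 and 9.5 and SAP section 5, and use the same anchor for the outcome and AESI window after a loss.

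If enrollment has closed, state in the report how sites applied the criterion, present losses and terminations by cohort and arm, and add the selection to the limitations in 4.5.

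The cost is one wording change carried through five protocol sections and one SAP section, plus record retrieval for the extra eligible women among the roughly 8240 already to be contacted. SAP 4.2.2 counts only pregnancies with medical records, so undocumented losses would stay missing even then.
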